- Arm A (Transition theory-based intervention): Women randomized to this arm will receive monthly one-on-one meetings with a community health worker for four months during late pregnancy and early postpartum
- Arm B (enhanced standard of care): Women randomized to this arm will receive one meeting with a community health worker in addition to the local standard of care.

[figure not shown]
Women randomized to each arm will be asked to attend two additional assessment study visits at 3- and 6-months postpartum. The primary outcome will be self-reported ART adherence and secondary outcomes will be retention in routine HIV care (from routine electronic medical records) and HIV viral load using dried blood spots.

Participation will have no impact on any aspect of women's routine antenatal and obstetric care during pregnancy, or on any aspect of their postpartum care. In addition, participation will have no impact on their routine HIV care. Women randomised to the Transition intervention will receive the intervention separate from any routine medical visits. Women randomised to the enhanced standard of care will attend all routine medical visits and will receive one meeting with a community health worker separate from any routine medical visits.

Aim 3: *Assess participants' experiences of the intervention, perceived usefulness, and identify ways to refine the intervention for future evaluation.*

This aim will be accomplished using in-depth individual interviews with all participants who were randomized to the intervention condition after all follow-up assessments have been completed (n= up to 30)

The study schema is summarized in the diagram below:

Setting

The proposed study will take place in the community of Gugulethu in Cape Town. Aim 1 was successfully conducted in this community and our team has actively collaborated with local

health services in this setting for over 10 years. The antenatal HIV prevalence rate in Gugulethu is between 26-30%. Participants will be recruited during pregnancy from the Gugulethu Midwife Obstetrics Unit (MOU), which is a public sector facility that serves more than 4800 pregnant and postpartum women annually.

4. Study Population

For Phase 2 of this study (Aims 2 & 3), inclusion criteria are as follows:

- 18 years of age or older
- HIV positive status (based on clinic records)
- Confirmed pregnant (based on clinic records) and estimated to be 23-34 weeks gestation (clinic records or self-report)

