A manual will be provided to the CHW. For the one-on-one sessions, the manual will describe possible areas to investigate where women may be having difficulties and information about procedures for referrals and availability of resources in the local area.

Educational materials will be adapted from the WHO and HHS/CDC Prevention of Mother-to-Child Transmission of HIV (PMTCT) Generic Training Package.⁵⁷ This training package was created as a comprehensive approach to the training of healthcare workers and provides guidelines for customized content to reflect local realities.

Process measures

The community health worker will complete logs for monitoring uptake and utilization of the intervention making note of session completion rates and dropouts. After individual sessions the CHW will also take extensive notes on topics focused on, common barriers experienced by women, and engagement within the sessions.

We will also audio record all counseling sessions to assess fidelity to the intervention. All counseling sessions will be coded using validated measures that have been adapted for this study.
 58 59

The following figure displays the differences in exposure between the Transition intervention and the enhanced standard of care as well as the assessments

| | Month 1 | Month 2 | Month 3 | Month 4 | Month 5 | Month 6 | Month 7 | Month 8 |
|--|---------|---------|--------------|--------------|--------------|--------------|--------------|--------------|
| | | | Postpartum 1 | Postpartum 2 | Postpartum 3 | Postpartum 4 | Postpartum 5 | Postpartum 6 |
| Assessments | | | | | | | | |
| Enrollment Appointment: Informed Consent, Baseline Survey Assessment, Locator Form | | X | | | | | | |
| Follow-up Quantitative Survey | | | | | X | | | X |
| Follow-up DBS | | | | | | | | X |
| Transition Intervention | | | | | | | | |
| One-on-one session with CHW | X | X | X | X | | | | |
| In-depth interviews | | | | | | | | X |
| Enhanced Standard of Care | | | | | | | | |
| One-on-one session with CHW | X | | | | | | | |

7. Study Procedures

The purpose of the study measurement visits will be to evaluate the study objectives. These study measurement visits will be carried out separately from any routine care, including antenatal, postpartum, or HIV-related care.

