Our team has extensive experience in utilizing data from routinely collected electronic medical records in this setting, including for ART and PMTCT outcome assessment.^{60,61} Data will be requested from the Western Cape Provincial Data Centre, and we will use participants' provincial folder number (requested as part of tracing information) to facilitate an accurate electronic data request. Permission to review electronic clinical records of participants will be included in informed consent documents. Following standard procedures, we will request approval from the Provincial Department of Health to access electronic medical records. Established procedures are in place to ensure patient confidentiality. The project manager will link these data to participants' unique participant identifiers.

For the primary outcomes obtained from routine medical records (engagement in care and HIV viral suppression), we will use the following definitions:

- Engagement in care will be classified as any evidence of engagement in routine HIV services, including evidence of: HIV visit attendance; ART collection at a pharmacy; laboratory testing of HIV viral load or CD4 cell count
- HIV viral suppression will be classified as a viral load <200 copies/mL

For the primary outcome, we will use a window of up to 3 months around the 6-month postpartum study visit. In cases where there is evidence of multiple HIV viral load results in this window, we will use the result closest to the 6-month postpartum study visit for the primary outcome. For women who are lost to follow-up, we will use the median time of visits attended among those who are retained at study measurement visits to assess engagement in care and HIV viral suppression. As the primary outcome data will come from routine medical records, all women will have outcome data regardless of retention at study measurement visits.

Routinely collected clinical data will be linked with the written permission of (a) the participant (via informed consent), (b) the research oversight body of the Provincial Government of the Western Cape including the Provincial Data Centre, and (c) the HREC. Established procedures are in place to ensure patient confidentiality.

Aim 3 Qualitative Component

In-depth interviews will be conducted with participants randomized to the intervention condition (n=up to 30) after the completion of follow-ups in order to assess participants' experiences of the

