intervention, perceived usefulness, and identify ways to refine the intervention for future evaluation. Participants will complete a separate informed consent form for the qualitative interview. Extra efforts will be made to capture participants who were not retained in the intervention to gain insight into elements of the intervention that may have contributed to disengagement from the intervention and to generate ideas for boosting retention in future evaluations.

The goal of these interviews is to evaluate the participants' views of the acceptability of the intervention and how useful they felt the intervention was with respect to medication adherence and retention in care. Content from these interviews will also allow us to better understand the quantitative outcomes of the intervention, regardless of the efficacy of the intervention. The in-depth interviews may also inform selection of future mediator or moderator variables to test in a full-scale RCT.

All study measures are detailed in the table below.

| | Measure | Enrolment | 3 months postpartum | 6 months postpartum |
|--|---|-----------|---------------------|---------------------|
| Quantitative component | | | | |
| Sociodemographic characteristics | Tool developed and used by our team previously ⁶⁰ | X | | |
| Pregnancy intentions | London Measure of Unplanned Pregnancy and measures of family planning use and fertility intentions ⁶³ Used by our team previously ⁶⁴ | X | X | X |
| Maternal health | Tool developed and used by our team previously ⁶⁰ Includes measures of self-reported health issues and health service use | X | X | X |
| Child questionnaire | Tool developed and used by our team previously ⁶⁰ Includes measures of breastfeeding, health issues and health service use | | X | X |
| Non-disclosure | Tool developed and used by our team previously ⁶⁵ | X | X | X |
| Partner questionnaire | Tool developed and used by our team previously Includes measures of relationship status, partner HIV testing, and partner substance use | X | X | X |
| COVID-19 impacts of engagement in care | Items are detailed below this table | X | X | X |
| Intimate partner violence | WHO Violence Against Women Questionnaire ⁶⁶ Used by our team previously ⁶⁷ | X | X | X |
| Depressive symptoms | Edinburgh Postnatal Depression Scale ⁶⁸ Used by our team previously ^{67 69} | X | X | X |

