| Substance use | Alcohol Use Disorders Identification Test ⁷⁰ Drug Use Disorders Identification Test ⁷¹ Both used by our team previously ^{67 72} | X | X | X |
| Adherence self-efficacy | Adherence Self-Efficacy ⁷³ Used by our team previously ⁷⁴ | X | X | X |
| Self-reported adherence | Tool developed and used by our team previously ⁷⁵ and the Visual Analog Scale ⁷⁶ Includes measures of side effects and self-reported adherence | X | X | X |
| Pregnancy and Postnatal Well-being in Transition Questionnaire | Validated tool that we adapted for HIV ⁴⁶ Includes measures of Transition Theory constructs | X | X | X |
| Alcohol-ART toxicity beliefs | Tool validated in Cape Town ⁷⁷ Includes measures of beliefs about mixing alcohol and ART | X | X | X |
| Routine medical data | | | | |
| Maternal health service use | Accessed from routine medical records | | X | |
| Infant health service use | Accessed from routine medical records | | X | |
| HIV viral load results | Accessed from routine medical records | | X | |
| Qualitative Component | | | | |

| | | |
|---------------------------|---|--|
| In-depth interviews (IDI) | IDI guide, conducted with all participants randomized to the intervention | After all study procedures and assessments have been completed |
|---------------------------|---|--|

COVID-19 impacts of engagement in care

1. Because of the COVID-19 pandemic, did you miss an appointment at your clinic for HIV treatment or care in the last 3 months? (Yes/No)
2. How do you access/have you accessed your ART tablets/your HIV medication during lockdown? (1=I buy them from someone on the street, 2=I get them from the clinic/hospital as I used to, 3= I borrow pills from a friend/household member/neighbor)
3. Has accessing your ART tablets/your HIV medications during lockdown been more challenging than before COVID-19? (Yes/No)
4. Are you worried that you will run out of ART tablets/your HIV medications because of challenges associated with COVID-19 (i.e. lockdown, don't want to go to the clinic during COVID-19) (Yes/No)

Identification of health needs during study procedures

At every study measurement visit, any woman found to have an unmet health need (whether medical, obstetric, postpartum family planning, or related to mental health or substance use) will be referred to the relevant service within the Gugulethu Community Health Centre or higher levels of care, as appropriate. In particular:

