There are several potential risks in participant in this study. Discussing sensitive topics such as pregnancy and HIV infection may cause psychological distress. Study staff will be trained in counseling and will continually monitor the participant for signs of distress. If signs of distress are apparent, the interviewer will offer to pause the session until the participant feels well enough to carry on. The participant will also be reminded that they may stop the session or un-enroll from the study at any time without penalty. If needed, referrals will be made to social services. We will also emphasize that participants may pause the interview at any time or may un-enroll from the study at any time without penalty.

To reduce risks of accidental disclosure of HIV status, all study activities (i.e. eligibility screening, interviews, assessments) will take place in a private room. During recruitment, eligibility questions will be embedded in a larger set of foil questions so that ineligible individuals will not be able to decipher why they were not eligible for the study. All data collected will not contain the name of the participant and will instead be identified by their unique PID number. All data will be stored in locked file cabinets and encrypted computers. Although this study is centered around HIV medications and adherence behaviors, study staff will not be prescribing medications and they will not change dosing of medications in any way. Optimal adherence to medications will always be encouraged. If the participant discloses issues with side effects or HIV symptoms, study staff will refer the participant back to their HIV care doctor.

Additionally, during the consent process, risks of breaches in confidentiality will be highlighted including legal norms that would require a break in confidentiality. All ethical issues requiring urgent attention will be reported to the PI immediately. All unanticipated ethical situations that do not need immediate attention will be discussing the weekly team meeting.

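### Under the Section 7 record window, records made after the interview held only in Arm A can count towards engagement in care and sometimes viral suppression; Sections 2, 3 and 7 must be reconciled

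*Combined protocol and SAP*

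**What the plan says.** **Interviews.** Section 3 (Phase 2, Aim 3) puts them after the end of follow-up: "This aim will be accomplished using in-depth individual interviews with all participants who were randomized to the intervention condition after all follow-up assessments have been" (sentence cut short here). The measures table in Section 7 gives the timing as "After all study procedures and assessments have been completed", with no latest date. The exposure grid at the end of Section 6 has the row "In-depth interviews | | | | | | | | X". Its mark falls under Month 8, Postpartum 6, and the row belongs to the Transition Intervention block. No interview is described for Arm B.

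**Reach and content.** Section 7 (Aim 3 Qualitative Component) says: "Extra efforts will be made to capture participants who were not retained in the intervention to gain insight into elements of the intervention". How and when these efforts are made is not described. One topic is "how useful they felt the intervention was with respect to medication adherence and retention in care". Section 10 (Potential Risks to Participants) says of the study in general: "Optimal adherence to medications will always be encouraged".

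**Record-based outcomes.** Section 7 (Linkage of routinely collected clinical data) states: "For the primary outcomes obtained from routine medical records (engagement in care and HIV viral suppression), we will use the following definitions". A single HIV visit, ART pick-up or HIV laboratory test is enough for engagement. On timing, "we will use a window of up to 3 months around the 6-month postpartum study visit". Where there are several viral loads, the one nearest the visit is used. Women lost to follow-up are given the median visit time of those retained.

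**Other definitions.** Section 2 defines retention by an HIV clinic appointment in the 3 months before the 6-month point, and takes suppression from clinic records without giving a window. Section 3 lists retention and viral load as secondary outcomes and takes viral load from dried blood spots, which the Section 6 grid schedules in Postpartum 6.

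**The concern.** The interview is a study contact that one arm gets and the other does not. It deals with adherence and staying in care, and particular effort goes into reaching Arm A women who stopped attending the sessions. If it prompts a woman to return to clinic while her record window is still open, the return is scored as engagement at 6 months although the counselling sessions did not produce it. A woman in the same position in Arm B gets no such prompt.

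The defence in Section 7 (Contamination and masking), that record-based outcomes are objective, does not cover this. Objective records guard against biased measurement. Here the unequal contact may change real attendance, which the records would capture faithfully.

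At stake is the pilot's estimate. Section 9 says the effect size and its direction will be used to support a larger trial, so a shift of a few points in a small arm matters even though no firm test is intended.

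**Working it through.** The plan gives no figure for this issue. Its power figures (Section 9) do not enter, so the check is one of timing, definitions and the weight of one woman.

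**1. Timing.** The interview comes after the 6-month visit, in Postpartum 6 on the grid. If the Section 7 window means 3 months either side, it runs from about 6 − 3 = 3 to 6 + 3 = 9 months postpartum, and about 3 months remain after the visit. If 3 months is the total width, about 3/2 = 1.5 months remain. On either reading, an interview held soon after the visit falls inside the window.

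**2. Definitions side by side.**

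| Source | Retention or engagement | Viral suppression | Can records after the interview count? |
|---|---|---|---|
| Section 2 | Clinic appointment, 3-month look-back; primary | Clinic records, no window; primary | Retention: no. Suppression: not settled |
| Section 3, Section 6 grid | Routine records, no window; secondary | Dried blood spot in Postpartum 6; secondary | Retention: not settled. Spot taken at the 6-month visit: no |
| Section 7 | Any HIV visit, ART collection or laboratory test in the window; primary | Result nearest the visit in the window; primary | Engagement: yes. Suppression: yes, if no nearer result exists |

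**3. Weight of one woman.** The Protocol Summary gives 43 randomised and Section 7 gives 1:1 allocation. Arm totals are not stated; an even split is 21 or 22. One change of status moves the Arm A rate by 100/22 = 4.5 or 100/21 = 4.8 points. At the planned 30 per arm it would be 100/30 = 3.3 points.

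**4. Illustration for engagement.** Shift = proportion out of care × proportion reached × proportion returning in the window because of the contact. The Introduction cites 49% disengaged by six months postpartum in Cape Town. The other two inputs are assumptions.
- Reach 80%, return 5%: 0.49 × 0.80 × 0.05 = 2.0 points.
- Reach 80%, return 30%: 0.49 × 0.80 × 0.30 = 11.8 points.
- Lowest case, reach 50%, return 5%: 0.49 × 0.50 × 0.05 = 1.2 points.
- Highest case, reach 100%, return 30%: 0.49 × 1.00 × 0.30 = 14.7 points.

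The 49% probably overstates the pool. A woman who left care in months 4 to 6 may already have a qualifying record before the visit, and her status then cannot change.

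**5. Direction for suppression.** Suppose k of m Arm A women with a result are suppressed, and a woman with no result gains one after the interview.
- If women without a result are left out, a suppressed result gives (k+1)/(m+1), which is above k/m when k < m. An unsuppressed result gives k/(m+1), which is below k/m when k > 0.
- If women without a result count as not suppressed, a suppressed result raises the rate and an unsuppressed one leaves it unchanged.

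Section 7 does not say which rule applies, and a woman returning after a gap may well be unsuppressed.

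**The case against.** The strongest reply is that the problem depends on one of three competing definitions. Section 2, the formal outcome list, looks back from 6 months, so a later contact cannot alter retention. A dried blood spot taken at the 6-month visit also precedes the interview. This stands, and it limits the point to the Section 7 window. It does not remove it, because Section 7 is the operational rule for the records and Section 2 gives no window for suppression.

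The shared procedures also count. Sections 7 and 8 provide tracing after missed measurement visits, and counselling or referral at those visits, in both arms. Section 8 says study staff trace only for missed measurement visits. Only the interview and the undefined extra effort are unequal. The interview is meant to collect views on acceptability and usefulness, and the Section 10 sentence on encouraging adherence is a general statement about the study. That the contact changes behaviour is plausible but not shown.

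Timing is loose too. The grid works in whole months and ends at Month 8, and the text sets no latest date, so some interviews may fall late in the window or after it. Nothing in the plan ensures that they do.

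A reader might infer that the women pursued are those out of HIV care. The documents do not say so: they are women not retained in the intervention, and missing sessions is not the same as leaving HIV care, though some overlap is likely. A reader might also infer that about half of Arm A (0.49 × 21.5 = 10.5 women) could be switched to engaged. The window already credits records before the visit, so that pool is too large.

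**Conclusion.** The point holds under the Section 7 record window. Records dated after a contact given only to Arm A can count towards engagement and, where no nearer result exists, towards suppression. For engagement, any bias from a prompted return favours Arm A. For suppression the direction is undetermined, so the reading that both outcomes are pushed towards the intervention is not supported.

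Each change of status is worth about 4.5 to 4.8 points in Arm A, assuming an even split of 43. The number of women affected is unknown, and the 1.2 to 14.7 point range rests on assumed reach and return, so it is not an estimate of bias.

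Self-reported adherence at the 6-month visit and session completion are unaffected. This is an avoidable asymmetry that should be closed, not a fatal flaw in an exploratory pilot.

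**What to change.** - Reconcile Sections 2, 3 and 7 on the rank of these outcomes, the evidence that counts as retention or engagement, the source of viral load and the window.
- For engagement, count record evidence in both arms only in the 3 months up to the 6-month visit date, or its assigned date if the visit was missed. Section 2 already uses this look-back, so the cost is almost nil.
- For suppression, choose one of two routes. Either hold each Arm A interview, and the contact to arrange it, until that woman's record window has closed; or make results dated up to the 6-month visit the main analysis in both arms, with the full Section 7 window as a sensitivity analysis.
- State how a woman with no viral load in the window is scored.

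The first suppression route means interviews up to about 3 months later, with some loss of recall and some attrition from the 24 interviews expected in Section 9. The second means fewer viral loads in the main analysis, but it is only an analysis rule and works even if interviews have already been held.
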